## **J. Statistical Methods**

**1. Power Analysis.** The primary goal of this Phase II study is to demonstrate sufficient superiority of rizatriptan over placebo in the main outcome measure, 1a(1), to warrant a future Phase III trial. In the previous triptan study for VM (see Prior Controlled Study of Triptans for VM), the response rate for active drug was 3/8 (38%) versus 2/9 (22%) for placebo. If the small sample from that failed trial reflected a true response, then the odds ratio favoring the triptan for VM would be 2.1. To improve our estimate, we examined the results of two large registration trials that used a simple randomization design similar to the present proposal to test rizatriptan for conventional migraine. Those studies had response rates of 74% and 77% for rizatriptan versus 28% and 37% for placebo giving odds ratios of 7.4 and 5.7 favoring rizatriptan. The lower response rates in the VM trial most likely reflected the inadequate sample size, but could suggest that triptans are less effective for VM than conventional migraine. To account for this possibility, we took the limited results of Neuhauser, et al. as a worst-case scenario for our sample size calculation. Focusing on the main outcome measure, 1a(1), in this double-blind, randomized trial, with PASS simple randomization design and using a type I error of 0.05, type II error of 0.2 (equivalent to power of 80%), two-sided tests, then treating 120 subjects (with 2:1 ratio for treatment and placebo) will allow us to detect an odds ratio as small as 3.2. Thus, the plan to enroll 200 subjects in the Observation Phase and select 120 for the Treatment Phase will be sufficient, even if the response of VM to rizatriptan proves to be only half that of conventional migraine. Phase II trials typically gather data on secondary outcomes (e.g., 1a(2)-1d(2)) and other variables (2a-c) to inform the design of Phase III trials, but sample sizes need not be planned to demonstrate significant differences in these variables.

**2. Randomization.** A randomization scheme will be developed to assign the 120 patients expected to be included in the Treatment Phase to parallel treatment arms in a 2:1 ratio of active drug:placebo.

**3. Statistical Analysis and Modeling.** We will use SAS and R^70 statistical software, creating ad hoc algorithms and macro procedures to solve analytical questions for which no marketed algorithms exist.

1. As a first step to understanding the nature of our data, we will conduct univariate analysis of demographics, primary and secondary outcome measures, illness-related variables (e.g., frequency, severity, and duration of vertigo attacks), associated symptoms, comorbid conditions, and self-report rating scales. The marginal distribution of each measure will be calculated at each time point and across time. The time trends of outcome measures will be evaluated by graphical analyses. For example, parallel plots for each of the outcome measures will be created to examine the patterns of change over time.

2. We will test the four hypotheses of Specific Aim #1 using bivariate methods and multivariate modeling. First, we will analyze differences between rizatriptan and placebo on all outcome measures at each time point using chi-squares to cross-tabulate categorical variables, and t-tests, analyses of variance (ANOVAs), or marginal regressions to compare continuous variables.

3. After testing bivariate differences, we will use repeated measures mixed effects models to compare outcome measures between rizatriptan and placebo over time, and examine the effects of covariates on treatment response. As an example, for the special case of binary outcome vertigo severity (Grade 3/2 versus Grade 1/0) and the more general case of ordinal outcome vertigo severity (Grade 3, 2, 1, 0), we will use SAS PROC GLIMMIX to model the logits of cumulative probabilities including vectors for study drug, illness related variables, associated symptoms, rating scales, random effects, and time. The estimates on the linear scale will represent log cumulative odds. The cumulative logits are formed as  $\log \{ \Pr(Y_i \leq j) / \Pr(Y_i > j) \} = X_i \alpha + Z_i \gamma_i + \varepsilon_i$  for  $i=1, \dots, n$ , where  $Y_i$  is the  $n_i \times 1$  vector of the outcome measure for the  $i^{\text{th}}$  patient,  $j=0,1,2,3$ ,  $n_i$  is the number of measurements for the  $i^{\text{th}}$  subject in the period,  $X_i$  is  $n_i \times p$  known predictors (indicator signifying rizatriptan and placebo, and time variable.) The fixed effects parameter vector of  $\alpha$  is  $p \times 1$ .  $Z_i$  is  $n_i \times k$  known predictors, which are associated with the random part of the model, including time-varying and time factors.  $\gamma_i$  is the  $k \times 1$  random effect parameter vector and  $\gamma_i \sim N(0, D)$ ,  $\varepsilon_i$  is  $n_i \times 1$  and  $\varepsilon_i \sim N(0, \sigma^2 I)$ , which is independent of  $\gamma_i$ . Let

$\Sigma_i(\theta) = Z_i D Z_i^T + \sigma^2 I$  with  $\theta$  being the parameter of covariance vector. Integrating out  $\gamma_i$  in the above random effect model, we can write  $Y_i \sim N(X_i \alpha, \Sigma_i(\theta))$ .

4. We will use this 3-step analysis procedure to test all outcome measures for hypotheses 1a-1d. However, the principal result of the study will be determined by the findings of bivariate analyses and multivariate modeling of the main outcome measure, 1.a.(1), plus favorable findings on tolerability measures, 1d(1)-1d(2). We will include all subjects who treat at least one vertigo attack with study drug (i.e., intent-to-treat analysis). A statistically significant result favoring rizatriptan over placebo on 1a(1) and absence of statistically significant differences on 1d(1)-1d(2) will support development of a Phase III clinical trial of rizatriptan for treating vestibular attacks in patients with VM. The design of future trials will also be informed by results of tests of secondary measures 1a(2)-1c(2). We did not hypothesize equal tolerability for rizatriptan and placebo, but rather an absence of significantly higher rates of serious adverse effects and drug-related treatment discontinuation, so our statistical analyses of measures 1d(1)-1d(2) will not include equivalence tests.

[figure not shown]
5. Analyses of Specific Aim #2 (a-c) will be descriptive and exploratory. As a Phase II trial, this proposed study is not powered for a thorough examination of covariates and confounds. We will start by reviewing univariate analyses of data collected during the Observation Phase of the study to identify results that will be critical for designing future Phase III trials. First, we will examine the distribution of VM attack frequency and severity (2a) to determine if these variables have normal, skewed, bimodal, or other distributions. This will allow future investigators to estimate recruitment patterns for Phase III studies. Second, we will establish a rank order of comorbid conditions (2b) by prevalence and likelihood of affecting the clinical course or treatment of VM. This will allow future Phase III investigators to understand trade-offs between strictness of subject selection criteria and generalizability of results. Third, we will establish a rank order of usual care and self-medication therapies for VM (2c). This will allow future investigators to establish criteria for allowable co-treatments in Phase III trials. Finally, we will repeat the multivariate modeling of step 3 above, including variables representing data 2a-c collected during the Treatment Phase of the study. Variables found to have significant or trend level effects on rizatriptan versus placebo treatment will mark design considerations for Phase III trials and potentially generate hypotheses for epidemiologic, mechanistic, or other lines of investigation of VM.

6. Missing Data: We do not anticipate a major problem with missing data from subjects who complete this study. Furthermore, repeated measures mixed effects models allow unbalanced data (e.g., missing follow-up data). Nevertheless, we will use the following approach to missing data. We will calculate the frequency and pattern of missingness of each measure as missing completely at random (MCAR), missing at random (MAR) or missing not at random (MNAR). Based on the nature of missingness, we will determine which imputation approach would be appropriate. For complex situations, we will use EM algorithm, fully Bayesian, maximum likelihood procedures, and parametric multiple imputation (MI) methods, which are appropriate under general MAR conditions. ML and MI tend to yield similar results when implemented in comparable ways. Nonrandom dropout may be a problem because subjects having the most severe attacks may object to taking placebo pills or seek alternative treatment. Subject demographics and illness characteristics can be used to test the MAR assumption. To reduce the possible impact of non-random dropout or MNAR missingness, subject characteristics variables will be used in the missing data model with MI/ML, which can reduce estimation bias due to MNAR missingness, and partially restore lost power due to missingness. We will examine the distribution of the outcome of interest (treated attacks in which subjects experience a reduction in severity rating) and the auxiliary variable, and apply joint modeling and MI methods to utilize the auxiliary information (e.g., subject characteristics). We will apply MNAR methods (e.g., selection models, pattern mixture models, and shared parameter models) to perform sensitivity analysis to evaluate model robustness.

7. Interim analysis: We will conduct an interim analysis at study midpoint without breaking the blind to assess (1) recruitment, (2) safety, and (3) efficacy. Plans for shortfalls in recruitment are noted below. We will terminate the study for insufficient safety if there is a statistically significant difference between arms in adverse events of greater than minor severity, or for lack of efficacy if response rates are <25% in both arms, i.e., no better than placebo rates in previous triptan trials. We will continue the study if the primary outcome, 1(a)1, is >25% in at least one arm, but not statistically different between arms. If the primary outcome is statistically different, then we will terminate the study because the primary aim will be met. We will break the blind and identify the results as positive (rizatriptan superior to placebo) or negative (rizatriptan inferior to placebo).

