## **L. Feasibility and Limitations**

The primary hindrance to successful completion of this study will be patient recruitment and retention. Rizatriptan has a proven track record of safety in thousands of patients over more than a decade of clinical use, so we do not expect significant problems with medication intolerance. The study of zolmitriptan by Neuhauser, et al., demonstrated the pitfalls of a triptan trial for patients with VM. Just 26% of enrolled subjects were randomized to treatment because they did not continue to have active vestibular attacks. We believe that we will substantially increase that randomization rate by enrolling only subjects with more active illness, as described in "Considerations for Improved Subject Selection for the Current Proposal." The previous investigators excluded 12% of subjects for coexisting medical problems. We expect to stabilize coexisting medical problems such as uncontrolled hypertension or anxiety disorders during our 12 month Observation Phase, allowing us to retain a higher percentage of enrolled subjects. Neuhauser, et al., also excluded 14% of subjects from randomization because they lived too far from the study center. Geographic barriers are much less of a problem for medical care in 2013 than they were in 2003. Both of our centers have expanded the reach of patient care through electronic communications and other secure technologies, eliminating the need for a geographic exclusion. These factors and the improvements in study design based on the five-point examination of shortcomings in the zolmitriptan trial (see "Prior Controlled Study of Triptans for Migraine-Associated Vertigo") should allow us to successfully randomize 50% of enrolled subjects into the Treatment Phase of this study. Keeping in mind that the sample size calculation reflected the worst-case scenario (100 subjects for the Treatment Phase), then we will have to recruit a maximum of 200 subjects into the Observation Phase. Our recently published studies indicate that we see approximately 200 new patients with VM at our two centers annually. A record review suggests that half of those would likely meet study inclusion criteria. Therefore, we expect to examine 400 potential subjects during the 4 years of active enrollment. Study success would require us to recruit 50% of those patients. The Mayo Clinic team has enrolled 79.3% of eligible patients into a currently active trial of sertraline versus verapamil for patients with VM/CSD, which demonstrates our ability to achieve needed enrollment. Subjects entering the current Mayo study have almost no experience with triptans. Most have been prescribed vestibular suppressants (e.g., meclizine) for acute attacks, meaning that we will lose almost no subjects due to prior rizatriptan treatment. (N.B. – The current Mayo study will not compete with this proposal. Its inclusion criteria target chronic, not acute, symptoms).

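### The sample size is described as set for a worst case (odds ratio 2.1), but the plan's own calculation reaches 80% power only at 3.2, and the enrolled and Treatment Phase counts conflict

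*Combined protocol and SAP*

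**What the plan says.** **Effect size (III.J.1 Power Analysis).** The prior trial's response rates were 3/8 on active drug and 2/9 on placebo. If they were true, "then the odds ratio favoring the triptan for VM would be 2.1". Two conventional migraine trials gave odds ratios of 7.4 and 5.7. The section says the lower response in the vestibular migraine trial "could suggest that triptans are less effective for VM than conventional migraine" and, to allow for that, takes its results "as a worst-case scenario for our sample size calculation". With two-sided alpha 0.05 and 80% power, it concludes that "treating 120 subjects (with 2:1 ratio for treatment and placebo) will allow us to detect an odds ratio as small as 3.2". It adds that this suffices even if the response is half that seen in conventional migraine.

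**Counts.**
- Specific Aims: 240 enrolled, about 120 randomised.
- III.J.1: "the plan to enroll 200 subjects in the Observation Phase and select 120 for the Treatment Phase will be sufficient".
- III.J.2 Randomization: the scheme is to "assign the 120 patients expected to be included in the Treatment Phase".
- III.L Feasibility and Limitations: the design "should allow us to successfully randomize 50% of enrolled subjects into the Treatment Phase of this study", and "the sample size calculation reflected the worst-case scenario (100 subjects for the Treatment Phase"; recruitment is capped at 200.
- IV.A.1 Number of subjects: 240 recruited.

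**Unit and population.** Main outcome 1a(1) in III Approach is a proportion of treated attacks. III.J.3 item 4 analyses subjects who treat at least one attack.

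**The concern.** If the prior trial is the worst case because triptans may work less well in vestibular migraine, a sample size set for it should have 80% power at OR 2.1. The stated detectable OR is 3.2, so the named worst case lies outside what the section says the trial can detect. III.L then repeats that the calculation reflected the worst case, and attaches a different number of subjects to it.

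This affects how a null result is read. III.M Plans to Address Limitations would treat a negative finding as evidence that rizatriptan lacks the efficacy to justify Phase III. How far that inference can be trusted depends on which effects the trial could have detected. A reader who accepts the worst-case description would put the chance of missing OR 2.1 at 20%.

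**Working it through.** **Inputs.** From III.J.1: two-sided alpha 0.05; 120 subjects at 2:1, so n1 = 80 and n0 = 40; placebo rates 2/9 (22%), 28% and 37%. The section does not print the control rate or the unit entered in PASS. One response per subject is inferred from its counting of subjects and from the match below.

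**Formulas.**
- Active rate: p1 = OR·p0 / (1 − p0 + OR·p0).
- Power = Φ{[(p1 − p0) − 1.96·s0] / s1}, where p̄ = (n0·p0 + n1·p1)/(n0 + n1), s0 = √[p̄(1 − p̄)(1/n0 + 1/n1)] and s1 = √[p0(1 − p0)/n0 + p1(1 − p1)/n1].

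**1. Reproduce the plan's figure (OR 3.2, p0 = 2/9).** p1 = 0.478, p̄ = 0.3925, s0 = 0.0946, s1 = 0.0863. Power = Φ[(0.2554 − 0.1853)/0.0863] = Φ(0.81) = 79%. The OR with exactly 80% power is 3.23. The stated 3.2 is confirmed.

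**2. The named worst case.** OR = (3/5)/(2/7) = 2.10, so p1 = 0.375, p̄ = 0.3241, s0 = 0.0906, s1 = 0.0852. Power = Φ[(0.1528 − 0.1776)/0.0852] = Φ(−0.29) = 38.5%. For 80% power, 321 treated subjects (107 + 214) would be needed.

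**3. Over the three placebo rates, one response per subject.**

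| | 22% | 28% | 37% |
|---|---|---|---|
| 120 treated, power at OR 3.2 | 79% | 83% | 84% |
| 120 treated, OR with 80% power | 3.23 | 3.08 | 2.99 |
| 120 treated, power at OR 2.1 | 39% | 43% | 47% |
| 100 treated (67 vs 33), power at OR 3.2 | 71% | 75% | 77% |
| 100 treated, OR with 80% power | 3.60 | 3.43 | 3.34 |

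The chance of missing OR 2.1 with 120 treated is therefore about 53% to 62%.

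**4. Attack-level power at OR 2.1.** Effective n per arm = n·m / [1 + (m − 1)·ICC], with every subject treating m attacks. The intraclass correlations (ICC) are assumptions; the plan gives none.

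| | 22% | 28% | 37% |
|---|---|---|---|
| m = 3, ICC 0.1 | 77% | 82% | 85% |
| m = 3, ICC 0.2 | 71% | 76% | 79% |
| m = 3, ICC 0.5 | 54% | 60% | 64% |
| m = 3, ICC at which power is 80% | 0.06 | 0.13 | 0.19 |
| m = 2, ICC 0 | 67% | 73% | 76% |

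Three attacks for every subject is an upper bound. III.K Timeline of Study closes follow-up however many attacks have been treated, and II.A reports that only 10 of 19 randomised subjects in the prior trial treated an attack, 17 attacks in all.

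**5. Counts.** 120/200 = 60%, which does not match the 50% randomisation rate in III.L. 0.5 × 200 = 100 and 0.5 × 240 = 120 do match it. Only 120 treated fits the stated OR 3.2. III.J.1 uses 120 for subjects treated and III.J.2 uses it for patients randomised, with no stated allowance for randomised subjects who treat no attack.

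**The case against.** The strongest case on the other side has four parts.

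- **The detectable OR is disclosed.** It is, and the figure is correct. The fault lies in the worst-case description.
- **Worst case may have meant only the control rate.** The 3.2 fits the prior trial's 22% placebo rate, the least favourable of the three cited. This is possible, but the reason given for using that trial is lower drug efficacy, which concerns the effect. If only the rate was borrowed, the text should say so.
- **The sufficiency claim is tied to half the conventional migraine response, not to OR 2.1.** On the odds-ratio scale this is only partly met. Half of 7.4 is 3.7, with 89% to 92% power. Half of 5.7 is 2.85, below 3.2, with 69% to 76% power. Half of their average is 3.28, with 81% power at 22% placebo. The clause limits what the section finally claims, but it does not make the worst-case statement true.
- **The outcome counts attacks, and the prior 3/8 and 2/9 were also attacks.** This is the best point, and it stands in part. With three attacks each and a low ICC, power at OR 2.1 reaches 80%. But the section counts subjects, claims no gain from repeated attacks and states no ICC. With two attacks each, power stays below 80% even at ICC 0.

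It is also fair to say that 240 enrolled with 120 randomised agrees with the 50% rate. The outliers are the 200 in III.J.1 and the 200 and 100 in III.L.

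**Conclusion.** The concern holds. The stated OR of 3.2 is right for 120 treated subjects, but the design is not sized for the worst case it names. Per subject, power at OR 2.1 is about 39% at the matching placebo rate and 39% to 47% over the three cited rates. Those figures rest on one response per subject, which is inferred. At attack level the shortfall could be smaller or nil, depending on quantities the plan does not state.

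The conflict in counts needs no assumption, since it can be read directly from the sections. Its consequence on the per-subject basis is that 100 treated would leave OR 3.2 with 71% to 77% power. The 225 observed and 114 randomised in the abstract at the end of the document are results and do not settle the planned numbers.

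This should be fixed. It is an error of description and consistency, not a flaw in the test or endpoint.

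**What to change.** 1. In III.J.1 and III.L, withdraw the statement that the sample size reflects the worst case. If only the prior trial's placebo rate was used, say that instead. State about 80% power at OR 3.2 and about 40% at OR 2.1 (39% to 47% by placebo rate) per subject, and name the placebo rate and unit entered in PASS.
2. Preferably, add attack-level power over a stated ICC range and expected number of attacks per subject, since the main outcome is counted in attacks.
3. Reconcile the enrolled (200 or 240) and Treatment Phase (100 or 120) numbers across Specific Aims, III.J.1, III.L and IV.A.1. State whether 120 means randomised or treating at least one attack. If it means randomised, state the power after the expected loss of those who treat none.

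The cost is text only. Endpoint, test, alpha and patient numbers stay as they are. The one drawback is that the stated power becomes less favourable.

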To accomplish these Specific Aims, we propose to enroll 240 patients diagnosed with VM from the busy tertiary neurotology practices at UCLA and Mayo Clinic into a 2-phase investigation consisting of an Observation Period of up to 12 months, followed by a Treatment Period of up to 3 treated episodes or end of study, whichever comes first. During the Observation Period we will prospectively characterize the frequency and severity of vestibular attacks and associated symptoms in VM, the prevalence and severity of comorbid conditions, and the use of abortive and prophylactic medications and non-prescription treatments in patients receiving usual clinical care. We will train patients to recognize vestibular spells appropriate for study treatment and stabilize potentially confounding comorbid conditions. We will measure subjects' satisfaction with usual care and their health-related quality of life. Approximately 120 persistently symptomatic subjects will be randomly assigned to treatment with either rizatriptan or placebo in a ratio of 2:1. We will measure the effects of study treatment on reducing or resolving vestibular and associated symptoms, reducing the need for additional symptomatic treatments, and improving treatment satisfaction and health related quality of life over the 48 hours that follow each treated attack. We will capture the incidence and severity of treatment-emergent adverse effects. The results will provide data to guide future Phase III study designs. They also may yield insights into pathophysiologic processes that cause VM and suggest directions for future mechanistic investigations.

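### The plan gives 200 or 240 enrolled and 100 or 120 randomised; at its own 50% yield, 200 enrolled gives 100, not the 120 treated behind the power statement

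*Combined protocol and SAP*

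**What the plan says.** Four parts of the protocol give sample-size figures.

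- **Specific Aims:** "we propose to enroll 240 patients diagnosed with VM from the busy tertiary neurotology practices", and "Approximately 120 persistently symptomatic subjects will be randomly assigned to treatment with either rizatriptan or placebo in a ratio of 2:1". Section IV.A.1 also gives 240 recruited.
- **III.J.1 Power Analysis:** "treating 120 subjects (with 2:1 ratio for treatment and placebo) will allow us to detect an odds ratio as small as 3.2", at 80% power and two-sided 0.05. It then says that "the plan to enroll 200 subjects in the Observation Phase and select 120 for the Treatment Phase will be sufficient".
- **III.J.2 Randomization:** "A randomization scheme will be developed to assign the 120 patients expected to be included in the Treatment Phase".
- **III.L Feasibility and Limitations:** the design improvements "should allow us to successfully randomize 50% of enrolled subjects into the Treatment Phase of this study". The worst-case calculation is then described as "100 subjects for the Treatment Phase), then we will have to recruit a maximum of 200 subjects into the Observation Phase". With 400 potential subjects expected over four years, "Study success would require us to recruit 50% of those patients".

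Section III.J.3, item 4, limits the analysis to subjects who treat at least one attack with study drug.

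**The concern.** III.J.1 and III.L attach different Treatment Phase sizes, 120 and 100, to the same worst-case calculation. III.J.1 also needs a 60% yield that no section states or defends. A maximum of 200 in III.L cannot be squared with 240 in the Specific Aims and IV.A.1.

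There is a second gap. The power statement counts subjects treated, but 120 is the number to be randomised. Subjects who have no treatable attack after randomisation leave the analysis, and no allowance is made for them.

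These figures serve as operating targets. Section III.M starts extra recruitment steps when enrolment or randomisation falls short of target, and V.E lists accrual being met as a ground for closing the study. Neither section gives the number meant. On the III.L figures both targets are met at 200 and 100, below the 120 treated that the power statement assumes.

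**Working it through.** **The chain**

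| Source | Enrolled | Randomised | Implied yield |
|---|---|---|---|
| III.J.1 | 200 | 120 | 120/200 = 60% |
| III.L | 200 (maximum) | 100 | 100/200 = 50% |
| Specific Aims | 240 | about 120 | 120/240 = 50% |

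At the stated 50% yield, 200 × 0.50 = 100 and 240 × 0.50 = 120. Recruiting 240 of the 400 candidates is 60%, not the 50% in III.L.

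**Reproducing the stated power.** Inputs from III.J.1 are two-sided 0.05, 2:1 allocation and odds ratio 3.2. III.J.1 gives no placebo rate with the 3.2. I assume 22%, from the earlier vestibular migraine trial it cites, and show 25%, 28% and 37% as a range (28% and 37% are the placebo rates it quotes from the registration trials). I also assume one outcome per subject, since III.J.1 makes no adjustment for repeated attacks.

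- Rizatriptan rate: odds = 3.2 × 0.22/0.78 = 0.9026, so p₁ = 0.9026/1.9026 = 0.474. The difference d is 0.254.
- Power = Φ[(d − 1.96·s₀)/s₁], where s₀ is the pooled and s₁ the unpooled standard error.
- 80 + 40 subjects: pooled rate 0.390, s₀ = 0.0944, s₁ = 0.0861; (0.2544 − 0.1850)/0.0861 = 0.81, power 79.0%. The detectable odds ratio at 80% power is 3.24.

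This agrees with the plan's 80% and 3.2, so the power figure itself is sound for 120 treated.

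**The same formula with fewer treated, odds ratio 3.2**

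| Treated (rizatriptan + placebo) | Placebo 22% | 25% | 28% | 37% |
|---|---|---|---|---|
| 120 (80 + 40) | 79.0% | 81.2% | 82.8% | 84.4% |
| 114 (76 + 38), 5% never treat | 76.7% | 79.1% | 80.7% | 82.5% |
| 108 (72 + 36), 10% never treat | 74.3% | 76.8% | 78.5% | 80.4% |
| 100 (67 + 33), III.L figure | 70.6% | 73.1% | 74.9% | 77.1% |
| 96 (64 + 32), 20% never treat | 68.9% | 71.5% | 73.4% | 75.5% |

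The 5%, 10% and 20% losses from 120 are assumed. With 100 treated, the detectable odds ratio at 80% power is 3.61 at 22% placebo and 3.34 at 37%.

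**Allowing for repeated attacks.** The primary outcome is a proportion of attacks, up to three per subject. With m attacks per subject and within-subject correlation ICC, the variance is multiplied by [1 + (m − 1)·ICC]/m. For 100 treated at 22% placebo:

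| | ICC 0.3 | ICC 0.5 | ICC 0.7 |
|---|---|---|---|
| m = 3 | 93.8% | 87.4% | 80.5% |
| m = 2 | 88.3% | 83.1% | 77.9% |

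The ICC values are assumed; the plan gives none.

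**Reported flow, for context only.** The results summary reports 114 of 225 randomised (50.7%), in line with 50% and not 60%. At up to three attacks each, 308 treated attacks need at least 308/3 = 102.7, so 103 of the 114 subjects (90%). These are outcomes and could not have informed the plan.

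**The case against.** The figure 100 appears once, in a section arguing that recruitment is feasible. The Specific Aims, the power statement and the randomisation section all say 120, and III.M and V.E name no number. Nothing says the trial would stop at 100, and the reported flow passed both 200 and 100. This stands as far as it goes: early closure is a risk only if the III.L figures are taken as the target.

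The fall to 71% also rests on one outcome per subject, whereas the trial analyses attacks with repeated-measures models. With three attacks each, 100 subjects keep at least 80% power at every ICC tried. This stands too, and 71% should not be read as the trial's power. But III.J.1 makes no per-attack calculation, so the plan cannot rely on one to justify its number.

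Finally, the 5% to 20% non-treatment range is not taken from the documents. Their one figure is far worse: in the earlier triptan trial 10 of 19 randomised subjects (53%) treated an attack. Two qualifying attacks before randomisation and a Treatment Phase of up to four years should reduce that loss. The size of the loss is therefore open; the absence of any stated allowance is not.

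**Conclusion.** The concern holds. The plan has two enrolment totals and two randomisation totals, and nothing reconciles them. Only 240 enrolled and 120 randomised fits both the 50% yield and the 120 behind the power statement.

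If the III.L figures were followed, power for an odds ratio of 3.2 would be about 71% to 77% instead of 79% to 84%, for placebo rates of 22% to 37% and one outcome per subject. With 120 randomised, the shortfall depends on a non-treatment rate that the plan does not state. Repeated attacks may restore 80%, depending on an attack count and correlation it does not state either. The power formula is not at fault. The figures around it should be corrected, because the trial's recruitment decisions depend on them.

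**What to change.** 1. Use one chain throughout: 240 enrolled × 50% = 120 randomised. Replace 200 in III.J.1 and III.L, and 100 in III.L.
2. In III.L, change the share to be recruited from 50% to 60% (240 of 400). That is still below the 75% and 79.3% enrolment rates the protocol cites from the other Mayo Clinic trial.
3. State the placebo rate used, and restate power or the detectable odds ratio for the number expected to treat at least one attack under a stated non-treatment allowance. Alternatively, show the per-attack calculation with a stated number of attacks per subject and within-subject correlation.
4. Name the enrolment and randomisation targets that III.M and V.E refer to.

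The cost is wording and one recalculation, with no patients beyond the 240 in the Specific Aims and IV.A.1. The restated power may be lower: at 22% placebo and one outcome per subject, 77%, 74% or 69% if 5%, 10% or 20% never treat. Keeping 120 treated under those losses would be a separate and dearer choice, at 120/(0.95 × 0.50) = 253, 120/(0.90 × 0.50) = 267 or 120/(0.80 × 0.50) = 300 enrolled.
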